## **11.4. Criteria for Evaluation and Statistical Methods**

### **11.4.1. Safety**

AE data will be summarized by counts and proportions of subjects having an AE, each AE type, and an AE of each System Organ Class. These summaries will be provided for the rhu-pGSN and placebo groups separately. SAEs will be summarized similarly. Reasons for any early discontinuations will be summarized similarly.

Laboratory data in relation to normal range values will be summarized via counts and percentages of subjects below, within, and above the respective normal range, and by summary statistics (N, mean, median, standard deviation, minimum, maximum, 90% confidence intervals, etc.) for baseline, each observed time point, and change from baseline at each observed time point for continuous lab endpoints.

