12.10.3 Laboratory Assessments

12.10.3.1 Continuous Summary

Descriptive summary of absolute result and change from baseline in laboratory data will be presented by parameter and visit for safety analysis set. Each category (Hematology, Clinical Chemistry and Coagulation) will be represented in separate tables. Note that Laboratory assessments will be done only if required by SOC.

In DDP: Tables 14.3.4.1, 14.3.4.2, and 14.3.4.3

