12.10.3.2 Categorical Summary

Number and percentage of subjects reporting laboratory interpretations (Normal, Abnormal Not CS and Abnormal CS, Not Done, Not required as per SOC) will be summarized by treatment, parameter, and visit. Each category (hematology, clinical chemistry, and coagulation) will be represented in separate tables. Percentages will be based on number of subjects with non-missing results in each visit within safety analysis set.

In DDP: Tables 14.3.4.4, 14.3.4.5 and 14.3.4.6

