12.10.3.3 Listings

All laboratory results will be listed for all subjects by visit and parameter. Out of range results will be highlighted.

In DDP: Listings 16.2.8.1, 16.2.8.2 and 16.2.8.3

Subjects with clinically significant laboratory results and subjects with out-of-range results will be separately listed by category, visit and parameter.

In DDP: Listings 16.2.8.4, Table 14.3.4.7

HIV and Pregnancy tests will only be listed by subject.

In DDP: Listing 16.2.8.5 and 16.2.8.6

Parameters collected in each laboratory category are listed below. In summaries and listings, parameters will be sorted in the order as below:

Category	Parameters
Hematology	Hemoglobin, Hematocrit, RBC, WBC, Platelet Count, Neutrophils, Lymphocytes, Monocytes, Eosinophils, Basophils, Reticulocyte Count,
Clinical Chemistry	Albumin, Alkaline Phosphatase, Alanine Aminotransferase (ALT), Aspartate Aminotransferase (AST), Bicarbonate, Direct Bilirubin, Total Bilirubin, Blood Urea Nitrogen, Lactate Dehydrogenase (LDH), Chloride, Creatine Phosphokinase (CPK), Creatinine, Amylase, Lipase, Potassium, Total Protein, Sodium, Ferritin, D-dimer, CRP, Procalcitonin, Urea, Total cholesterol (TC), HDL-C, LDL-C, Triglycerides
Coagulation	PT, PTT, aPTT, International Normalized Ratio (INR)

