12.10.4.3 Electrocardiogram Assessments

Descriptive summary of absolute result and change from baseline in EKG Results will be presented by treatment, parameter and visit for Safety analysis set. The parameters to be presented are: Heart Rate (beats/min), PR (msec), RR (sec), QRS (msec), QT (msec) and QTcF (msec). Note that EKG assessment will be done only if required by SOC.

Number and percentage of subjects with findings (Normal, Abnormal Not CS, Abnormal CS, Not Done, Not Required as per SOC) will be summarized by treatment, parameter, and visit. Percentages will be based on safety analysis set.

In DDP: Table 14.3.5.3 and Table 14.3.5.4

EKG Findings will be listed by subject and visit.

In DDP: Listing 16.2.9.3

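### The SAP's categorical laboratory table drops the protocol's low/in-range/high counts without declaring it, and gives its untested rows a denominator that excludes them

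*SAP*

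**What the plan says.** **Protocol.** Section 11.4.1 (Safety) says laboratory data will be "summarized via counts and percentages of subjects below, within, and above the respective normal range". It also promises summary statistics for continuous laboratory variables at baseline, at each time point and as change from baseline, and names 90% confidence intervals among them.

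**SAP, categorical table.** Section 12.10.3.2 reports "Number and percentage of subjects reporting laboratory interpretations (Normal, Abnormal Not CS and Abnormal CS, Not Done, Not required as per SOC", by treatment, parameter and visit. On the denominator it states: "Percentages will be based on number of subjects with non-missing results in each visit within safety analysis set".

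**SAP, other laboratory output.**
- Section 12.10.3.1 summarizes absolute results and change from baseline. It adds: "Note that Laboratory assessments will be done only if required by SOC". The statistics come from section 8.1 (n, mean, SD, IQR, minimum, maximum, median), which has no confidence interval.
- Section 12.10.3.3 highlights out-of-range values in the listings and says "subjects with out-of-range results will be separately listed by category, visit and parameter".
- Section 11.3.3 names only the WHO severity score and CURB-65 as needing shift summaries.
- Section 13 declares two changes from the protocol: the daily WHO score and the external-control comparison. Neither concerns laboratory data.

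**SAP, parallel table.** The EKG findings table (12.10.4.3) also has Not Done and Not Required rows. There the rule is: "Percentages will be based on safety analysis set". The physical examination table (12.10.4.2) has a Not Done row and uses the same set.

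**The concern.** There are two separate defects in one table.

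**Direction.** The protocol's classification keeps low and high apart. The SAP's does not: a low platelet count and a high one both count as abnormal. Many of the tests listed in SAP 12.10.3.3 (white cells, platelets, sodium, potassium) can be abnormal in either direction. Subjects also enter with raised ferritin, D-dimer or CRP, so movement from high into range and movement from in-range to low are both plausible. What is at stake is a by-arm safety count that the protocol committed to and that nothing else described in the SAP supplies.

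**Denominator.** Subjects who were not tested appear in the numerator of two rows but, on the plain reading, are excluded from the denominator. Testing depends on standard of care, so some untested subjects are to be expected. The printed percentages would then not describe a proportion of anything.

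**Working it through.** The documents state no figure for this point, so there is none to reproduce.

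**Step 1: classification, side by side.**

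| Output | Low and high separated? | Counted by arm? |
|---|---|---|
| Protocol 11.4.1 range counts | yes | yes |
| SAP 12.10.3.2 categorical table | no | yes |
| SAP 12.10.3.1 absolute and change summaries | direction of the average only | not as counts |
| SAP 12.10.3.3 listings | yes | listed by subject |

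No SAP output in this table both separates low from high and counts subjects by arm.

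**Step 2: what pooling does (hypothetical counts).**
- *Between arms.* Suppose 20 are tested per arm, with 8 low in one arm and 8 high in the other. The SAP table shows 8/20 = 40% abnormal in both. The protocol's table shows 40% against 0% below range, and 0% against 40% above. If those 8 subjects each moved by d from in-range values and nobody else changed, the mean changes are −8d/20 = −0.4d and +8d/20 = +0.4d. The continuous summary would therefore reveal the difference.
- *Within an arm.* Take 30 tested: 12 high, 18 in range, 0 low at baseline. Six then move from high into range and six from in-range to low. Abnormal is 12/30 = 40% at baseline and (6 + 6)/30 = 40% afterwards. Range counts show high going from 40% to 6/30 = 20%, and low from 0% to 6/30 = 20%. All 12 moves are downward, so the mean would normally fall. A falling mean alone does not say how many subjects normalized and how many dropped below range.

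**Step 3: denominator.** Let T be the number tested and U the number untested. Taken literally, the untested rows together print U/T, and the whole column totals (T + U)/T. Inputs: 30 per arm from Protocol 7.1 (Part 1), taken as the size of the safety set. T is not given in the documents, so it is varied.

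| Tested T | Untested U | Untested rows combined, U/T | Column total | U/30 (safety-set denominator) |
|---|---|---|---|---|
| 30 | 0 | 0.0% | 100.0% | 0.0% |
| 27 | 3 | 11.1% | 111.1% | 10.0% |
| 20 | 10 | 50.0% | 150.0% | 33.3% |
| 15 | 15 | 100.0% | 200.0% | 50.0% |
| 14 | 16 | 114.3% | 214.3% | 53.3% |
| 10 | 20 | 200.0% | 300.0% | 66.7% |

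The column passes 100% as soon as one subject is untested. A single row passes 100% only if its own count exceeds T. Even with the two untested rows combined, that needs fewer than half tested. With 10 tested, 8 Not Done and 12 Not required, the rows read 8/10 = 80% and 12/10 = 120%.

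**The case against.** - **The signal is not lost.** A reader might infer that opposite shifts cancel and disappear. The documents do not support that. Section 12.10.3.1 still reports mean, spread, extremes and change from baseline, and out-of-range values are highlighted and listed. The shifts are pooled in one table. This objection stands against the stronger reading. What it leaves untouched is the missing by-arm count of low and high values.
- **The clinical-significance classes belong there.** The secondary safety endpoint (Protocol 5.2.2, SAP 7.2.1) concerns new or worsening clinically significant laboratory abnormalities, and the SAP's classes relate directly to it. This stands: range counts should be added, and the classes kept. A by-visit count without a comparison to baseline does not by itself show new or worsening.
- **The denominator may only be loosely worded.** If a recorded Not Done or Not required entry counts as non-missing, the rows sum to 100%. The text allows this, so percentages above 100% are conditional. The sentence still needs correcting, because its plain meaning conflicts with the rows and with the EKG table.
- **The layout may be settled elsewhere.** SAP 12.10.3.3 cites a Table 14.3.4.7 whose format is in the Data Display Plan, which is not among the documents. The SAP text cites it only under listings, so it cannot be taken as the protocol's range table.
- **Who makes the call.** It is tempting to say the table rests on investigator opinion in place of laboratory limits. SAP 12.10.3.2 does not say who interprets. Protocol 9.2.6 gives clinical significance to the investigator, but nothing says that normal versus abnormal ignores the reference range. Nor does the table raise any blinding problem.

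**Conclusion.** The point holds in a limited form. The SAP omits the protocol's low/in-range/high counts and its 90% confidence intervals for continuous laboratory data, and section 13 does not say so. The remaining outputs do not provide a by-arm count of values newly below or above range. Separately, the stated denominator does not fit the untested rows. On the plain reading, column totals run from 111% with 27 of 30 tested to 150% with 20 of 30. These totals rest on an assumed 30 per arm and an assumed number tested; the documents give no testing rate.

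The size is minor to moderate. These are descriptive tables with no hypothesis test attached, the primary safety endpoint is the incidence of SAEs, and all laboratory values are kept and listed. It still merits correction, because safety is a primary objective and the departure from the protocol is undeclared.

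**What to change.** 1. In SAP 12.10.3.2, add the number and percentage of subjects below, within and above the reference range, by arm, parameter and visit (baseline included), with the number tested as denominator.
2. Keep the Normal / Abnormal Not CS / Abnormal CS classes, on the same denominator.
3. Show Not Done and Not required as per SOC as counts only, or as a percentage of the Safety Analysis Set as in the EKG table. State the denominator for each block of rows.
4. Add the 90% confidence interval to the continuous summary in 12.10.3.1, or declare its omission with a reason in section 13.

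The cost is SAP wording and one added table, or added rows, for each of the three laboratory categories. Out-of-range results are already to be highlighted, so reference ranges are needed anyway. No new data are required.

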12.10.3.3 Listings

All laboratory results will be listed for all subjects by visit and parameter. Out of range results will be highlighted.

In DDP: Listings 16.2.8.1, 16.2.8.2 and 16.2.8.3

Subjects with clinically significant laboratory results and subjects with out-of-range results will be separately listed by category, visit and parameter.

In DDP: Listings 16.2.8.4, Table 14.3.4.7

HIV and Pregnancy tests will only be listed by subject.

In DDP: Listing 16.2.8.5 and 16.2.8.6

Parameters collected in each laboratory category are listed below. In summaries and listings, parameters will be sorted in the order as below:

Category	Parameters
Hematology	Hemoglobin, Hematocrit, RBC, WBC, Platelet Count, Neutrophils, Lymphocytes, Monocytes, Eosinophils, Basophils, Reticulocyte Count,
Clinical Chemistry	Albumin, Alkaline Phosphatase, Alanine Aminotransferase (ALT), Aspartate Aminotransferase (AST), Bicarbonate, Direct Bilirubin, Total Bilirubin, Blood Urea Nitrogen, Lactate Dehydrogenase (LDH), Chloride, Creatine Phosphokinase (CPK), Creatinine, Amylase, Lipase, Potassium, Total Protein, Sodium, Ferritin, D-dimer, CRP, Procalcitonin, Urea, Total cholesterol (TC), HDL-C, LDL-C, Triglycerides
Coagulation	PT, PTT, aPTT, International Normalized Ratio (INR)

12.10.4 Other Safety Analyses

12.10.4.1 Vital Signs

Descriptive summary of absolute result and change from baseline in vital signs will be presented by treatment, parameter and visit for Safety analysis set. Parameters to be included: Weight (kg), BMI (kg/m²), Systolic Blood Pressure (mmHg), Diastolic Blood Pressure (mmHg), Respiratory rate (breaths/min), Heart rate (beats/min) and Temperature (°C). In summaries and listings, parameters will be sorted in the order mentioned.

In DDP: Table 14.3.5.1

Vital signs will be listed by subjects and visit for safety analysis set.

In DDP: Listing 16.2.9.1

12.10.4.2 Physical Examination

Number and percentage of subjects with results (Normal, Abnormal Not CS, Abnormal CS, Not Done) will be summarized by treatment, body system and visit. Body systems to be summarized are: Skin, HEENT, Neurologic, Lungs, Abdomen, and Heart. Percentages will be based on safety analysis set. Any additional body systems assessments as 'Other' will be listed and not summarized.

In DDP: Table 14.3.5.2

Physical Examination will be listed by subject and visit.

In DDP: Listing 16.2.9.2

12.10.4.3 Electrocardiogram Assessments

Descriptive summary of absolute result and change from baseline in EKG Results will be presented by treatment, parameter and visit for Safety analysis set. The parameters to be presented are: Heart Rate (beats/min), PR (msec), RR (sec), QRS (msec), QT (msec) and QTcF (msec). Note that EKG assessment will be done only if required by SOC.

Number and percentage of subjects with findings (Normal, Abnormal Not CS, Abnormal CS, Not Done, Not Required as per SOC) will be summarized by treatment, parameter, and visit. Percentages will be based on safety analysis set.

In DDP: Table 14.3.5.3 and Table 14.3.5.4

EKG Findings will be listed by subject and visit.

In DDP: Listing 16.2.9.3

12.10.5 Exploratory Analyses

Exploratory analyses looking at biomarkers and outcomes in each treatment arm will be conducted. The decision on whether biomarker results will be analyzed, and list of biomarkers to be analyzed will be made after database lock.

13 Changes to Planned Analyses

- One of the Secondary Efficacy Endpoints as per protocol is “Daily change in 9-point WHO severity score through at least Day 14”. Since the WHO Severity Score is required only on Days 1, 2, 3, 7 and 14 (on other days, it is not mandatory), the analysis of the WHO Severity score will be done for “Change in 9-point WHO severity score through Day 14 on scheduled visits”. All WHO Severity scores will be listed.
- Exploratory analysis to compare the efficacy endpoint data from the rhu-pGSN group from this study to that of external control data was not considered feasible at the time of database lock, so this analysis will not be performed.

14 Index of Tables, Listings and Graphs

Refer BTI_Data Display Plan (Ver: 1.00) for the list of Tables, Listings and Graphs.

15 References

Provide list of references used to create this document.

- ICH. ICH Harmonized Tripartite Guideline: Statistical Principles for Clinical Trials E9. 1998.
- ASA. Ethical Guidelines for Statistical Practice. Prepared by the Committee on Professional Ethics. 1999.
- ICH. ICH Harmonized Tripartite Guideline: Structure and Content of Clinical Study Reports E3. 1995.
- BTI-201 CSR v1.0 Final 24Dec2019_signed (Phase 1 study protocol)
- BTI-201-Statistical-Anal-PF-v2-Amen-1_2018-12-03 (Phase 1 study SAP)
- CONSORT 2010 Explanation and Elaboration: updated guidelines for reporting parallel group randomised trials

16 Appendices

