### 5.2.2. Secondary Endpoints

- Safety and tolerability
  - Incidence, causality, and severity of AEs (graded according to the National Cancer Institute [NCI] Common Terminology Criteria for Adverse Events [CTCAE] version 5.0) in rhu-pGSN vs placebo groups
  - Frequencies of new or worsening clinically significant laboratory abnormalities in rhu-pGSN vs placebo groups
  - Mortality rate irrespective of cause at Days 28 and 90
- Efficacy
  - Daily change in 9-point WHO severity score through at least Day 14 (including after discharge, where feasible)
  - All-cause mortality at Days 28 and 90; time to death (Kaplan-Meier survival analysis)
  - Proportion of subjects alive on Days 7, 14, 28, 60, and 90 without:
    - Ongoing use of vasopressors
    - Ongoing intubation/mechanical ventilation
    - Ongoing residence in an ICU
    - New ongoing need for dialysis/renal replacement therapy (RRT)
  - Proportion of subjects discharged to home or immediate prior residence by Day 28
  - Days on the ventilator
  - Length of stay (LOS) in hospital and in ICU (days)
  - Re-admission to an acute-care hospital up to Day 90
- PK
  - PK for rhu-pGSN including maximum concentration ( $C_{max}$ ), time to maximum concentration ( $T_{max}$ ), terminal half-life ( $T_{1/2}$ ), area under the curve from time zero to 8 hours ( $AUC_{0-8}$ ), area under the curve from time 0 to infinity ( $AUC_{inf}$ ) for Dose #1 within 15 minutes predose, and at 1 ( $\pm 15$  min), 2 ( $\pm 15$  min), 6 ( $\pm 30$  min), and 12 ( $\pm 30$  min) hours after end of administration (but prior to Dose #2); for Dose #3 within 15 minutes predose, and at 1 ( $\pm 15$  min), 2 ( $\pm 15$  min), 6 ( $\pm 30$  min), 12 ( $\pm 30$  min) and 24 ( $\pm 30$  min) hours after the end of administration (participants refusing these blood samplings can enter and remain in the trial).
- Immunogenicity
  - Presence of anti-pGSN antibodies on Days 1 (predose), 28, and 90

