## **6.6. Total Duration of Subject Participation**

Subjects will be observed for the primary efficacy endpoint with daily assessments (including WHO severity score) from Day 1 through Day 14. If a subject is discharged prior to Day 14, he/she will be assessed, if feasible, by phone daily through Day 14, and then at follow-up visits, on Days 28, 60, and 90, and as needed.

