Abbreviations: AEs=adverse events; CBC=complete blood count; Con meds=concomitant medications; CRP=C-reactive protein; CT=computed tomography; CURB-65=Confusion, Urea >7 mmol/L, Respiratory rate ≥ 30/min, Blood pressure systolic <90 or diastolic ≥60, and age ≥65 years (score); CXR=chest x-ray; EKG=electrocardiogram; HIV=human immunodeficiency virus; IL=interleukin; INR=international normalized ratio; PEEP=positive end-expiratory pressure; PK=pharmacokinetic; PT=prothrombin time; aPTT=activated partial thromboplastin time; RT-PCR=reverse transcription polymerase chain reaction; SOC=standard of care; Term=termination; TNF=tumor necrosis factor; WHO=World Health Organization.

a Day 1 is the first day of study treatment. Baseline tests (including blood draws) should be performed prior to administration of the first dose. Screening tests may also be performed on Day 1 prior to study treatment if necessary, as long as these tests cannot affect eligibility. If Dose 1 is administered in the evening of Day 1, Dose 2 would be given on the second calendar day and Dose 3 would be given on the third calendar day,

b Test/assessment does not have to be repeated if performed within the prior 24 hours unless dictated by SOC.

c Assess daily from screening through Day 14 during hospitalization and after discharge, where feasible, and then at Days 28, 60, and 90.

d Collect sputum sample as soon as possible if not collected at the time of hospital admission. The microbiology lab is encouraged to also perform sputum Gram-stains, antigen detection, immunoassay, and RT-PCR diagnostic tests when available. If fevers or chills are present, 2 sets of blood cultures are recommended at the discretion of the caregivers.

e To be performed if/when indicated by SOC.

f At screening, document radiographic evidence (CXR, or CT scan if CXR is inadequate) of COVID-19 pneumonia if not already completed in the previous 48 hours per SOC. On Days 14 and 28, repeat RT-PCR for COVID-19 and repeat CXR, or CT scan if CXR is inadequate, are encouraged but not mandatory.

g Height and weight only to be measured at screening or baseline and as per SOC thereafter. In Part 2, height is not required at screening and weight may be obtained via bed scale, if possible, or estimated.

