### **9.1.1. WHO Severity Score**

During screening and at the time points presented in the Schedule of Assessments ([Table 5](#)), each subject's WHO severity score according to the 9-point scale (Section [6.1](#)) will be recorded on the appropriate eCRF. WHO severity scores should be documented daily through Day 14 (during hospitalization and after discharge, where feasible).

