## 11. STATISTICS

### 11.1. General Overview

All subjects given e 1 dose of study drug will be included in the Full Analysis Set (FAS) according to actual drug received; non-completers will be counted as failures in the primary efficacy analysis. Subjects receiving all 3 doses and evaluable for the primary Day 14 endpoint will constitute the per-protocol population for efficacy assessment. WHO severity score will be recorded daily while the subject is hospitalized, after discharge through Day 14, where feasible, and at each follow-up visit.

AE data will be summarized for the FAS by actual drug received using counts and proportions of subjects having an AE, each AE type, and an AE of each System Organ Class. SAEs and reasons for any early discontinuation will be summarized similarly. All deaths will be categorized by cause of death as per investigator assessment and relationship to study drug and/or COVID-19

Immunogenicity will be assessed on Days 1(predose), 28, and 90 days in all participants. Antibodies against pGSN will be assayed from frozen specimens to determine whether the investigational product induces an antibody response in recipients.

For Part 1, binary efficacy endpoints will be compared between treatments via stratified Cochran-Mantel-Haenszel (CMH) test and, to accommodate continuous covariates, via logistic regression. Continuous efficacy and biochemical endpoints will be compared between treatments via mixed model repeated measures analysis or analysis of covariance, depending on whether repeated measures are available or not. Time-to-event analysis via stratified log rank test and Cox proportional hazards model may also be carried out as supplemental analyses.

For Part 1, exploratory analyses looking at biomarkers and outcomes in each treatment arm will be conducted. Other exploratory analysis to compare the efficacy endpoint data from the rhu-pGSN group from this study to that of external control data may be carried out if appropriate. Sample size may be increased to improve the precision of the estimates of between-treatment comparisons if appropriate and if drug supplies are available.

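### SAP Section 13 replaces the daily WHO-score endpoint with a scheduled-visit version on an incorrect premise, so 9 of the 13 post-baseline days through Day 14 are listed but not analysed

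*SAP*

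**What the plan says.** Protocol Section 5.2.2 (and the synopsis) lists this secondary efficacy endpoint: "Daily change in 9-point WHO severity score through at least Day 14 (including after discharge, where feasible"). SAP Section 7.2.2 repeats it as a daily endpoint, without the words on discharge.

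The protocol sets the collection rule in four places:

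- Section 6.6: "daily assessments (including WHO severity score) from Day 1 through Day 14", with telephone assessment after an early discharge if feasible.
- Table 5, footnote c, attached to the WHO row: "Assess daily from screening through Day 14 during hospitalization and after discharge, where feasible, and then at Days 28, 60, and 90".
- Section 9.1.1: "WHO severity scores should be documented daily through Day 14 (during hospitalization and after discharge, where feasible").
- Section 11.1: "WHO severity score will be recorded daily while the subject is hospitalized, after discharge through Day 14, where feasible, and at each follow-up visit".

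SAP Section 13 (Changes to Planned Analyses) gives its premise as "Since the WHO Severity Score is required only on Days 1, 2, 3, 7 and 14" and adds that other days are not mandatory. It substitutes the endpoint "Change in 9-point WHO severity score through Day 14 on scheduled visits" and says of the remaining data: "All WHO Severity scores will be listed".

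The SAP analyses follow from this. The shift summary and box plot (Section 12.9.2.1) use Days 2, 3, 7, 14, 28, 60 and 90, and the mixed model for repeated measures takes scheduled-visit scores only. The SAP assessment schedule (Section 5) shows the WHO row without the protocol's daily footnote.

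**The concern.** A SAP may narrow a protocol endpoint if it says so and gives a sound reason. Here the change is declared, but the only reason offered does not match the protocol in force. Protocol v4.0 is dated 09 June 2021 and SAP v1.00 is dated 05-Aug-2021, so the daily requirement already stood when the SAP was approved.

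Two things are at stake. First, a named secondary endpoint is not analysed in the form the protocol gives it, although the protocol asks sites to collect the scores it needs. Second, a study report that carries the Section 13 wording forward would tell readers that daily scores were not required.

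The four days that remain are also unevenly spaced. Doses are given at 0, 12 and 36 hours, and Table 5 footnote a allows Dose 3 to fall on the third calendar day. Days 2 and 3 therefore lie within the dosing period or just after it. From Day 4 to Day 14, only Days 7 and 14 are analysed.

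**Working it through.** **Step 1: is the premise right?** Take the two situations a subject can be in on a non-visit day such as Day 5 or Day 10.

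- *In hospital.* Protocol Sections 6.6, 9.1.1 and 11.1 and Table 5 footnote c all call for a daily score. None of them makes it optional for an inpatient. The synopsis (Duration of subject participation) also has daily assessment, WHO score included, from Day 1 until discharge. The SAP premise is wrong here.
- *Discharged.* Footnote c and Sections 9.1.1 and 11.1 ask for daily scores where feasible, and Section 6.6 makes the daily calls conditional in the same way. The SAP's remark that other days are not mandatory is fair here.

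**Step 2: could an older protocol version explain it?** The change summary for v2.0 to v3.0 (29 January 2021) shows footnote c being added. The SAP schedule lacks that footnote, which is consistent with its having been taken from an earlier Table 5. The superseded text in the same summary already called for daily recording while the subject was in hospital. The amendment added the post-discharge days, so the premise fails for inpatients under either version.

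**Step 3: how many days are affected?**

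- Baseline is Day 1 (Protocol Section 6.1), so the post-baseline days through Day 14 are Days 2 to 14: 14 − 1 = 13.
- Days analysed under the SAP (Section 12.9.2.1): 2, 3, 7 and 14, which is 4.
- Days only listed: 4, 5, 6, 8, 9, 10, 11, 12 and 13, so 13 − 4 = 9.
- Share only listed: 9/13 = 0.692, or 69%.
- From Day 4 to Day 14 there are 11 days, of which 2 are analysed. The longest gap is Days 8 to 13, six days.

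**Step 4: do visit windows change the count?** The schedule allows Day 7 ± 1 and Day 14 ± 2, so a score from a neighbouring day may stand in for a scheduled visit. This can change which calendar day is used, but a subject still contributes at most four post-baseline scheduled-visit values for Days 2, 3, 7 and 14.

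The plan states no figure of its own on this point, so there is none to reproduce.

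**The case against.** The case for leaving the SAP as it is has real content.

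- *The change is open.* It sits in the section meant for such changes, the score is still analysed by three methods, and every value is listed. This stands. A reader might infer that the endpoint has been dropped, but the documents show it replaced by a version with fewer time points.
- *The premise is partly true.* It is, for discharged subjects on non-visit days. It is not true for inpatients, and Section 13 draws no such distinction.
- *The daily scores may be patchy.* They may be. The protocol asks for them, but nothing shows how many exist. Subjects enrolled before v3.0 may have no daily scores after discharge. A reader might infer that a full daily data set is lying unused, and the documents do not establish that. If completeness was the real reason, Section 13 should say so.
- *69% of days is not 69% of information.* This stands. Scores within a subject are likely to be correlated, and the Day 7 and Day 14 contrasts are still estimated. No loss of precision can be calculated from the documents, nor do they show that the omitted days are when most patients worsen or recover.
- *Timing is covered elsewhere.* In part. The SAP compares hospital, ICU and ventilator days, time to death, survival without support at set days, and discharge. None of these is the daily WHO score.
- *Daily modelling is impractical.* An unstructured matrix for 13 visits has 13 × 14 / 2 = 91 covariance parameters, against 60 planned Part 1 subjects. This is a good reason to model fewer visits. It is not a reason to leave the daily scores without any by-treatment summary.

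**Conclusion.** The point holds in a limited form. The reason given in SAP Section 13 is incorrect for hospitalised subjects. Because of the change it supports, 4 of the 13 post-baseline days through Day 14 enter the summaries and the model, while 9 are only listed. The count takes Day 1 as baseline and the SAP's named visit days at face value.

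The effect on precision is unknown and may be modest. The completeness of the unanalysed scores is also unknown. This is one of several secondary endpoints in a proof-of-concept trial, and SAP Section 8.2 already asks for caution in reading secondary tests. The primary endpoint, sample size and power are untouched. It should be corrected because the stated rationale is wrong and the remedy is cheap. The documents do not support reading the change as concealment or as the loss of the endpoint.

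**What to change.** 1. In SAP Section 13, replace the rationale. State that the protocol requires daily scores through Day 14 in hospital and where feasible after discharge. If the mixed model stays on scheduled visits, give the true reason, for example the number of covariance parameters or the expected gaps after discharge.
2. In the SAP schedule (Section 5), restore the daily footnote to the WHO row.
3. Add a by-treatment analysis of the daily scores for Days 2 to 14. At the least, show score and change from baseline for each day with the number observed. Carry death as 8 from the day of death, and write down a rule for missing days after discharge. The number observed will itself show how complete the data are.
4. Keep the scheduled-visit mixed model as planned.

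A per-subject mean of the daily scores over Days 2 to 14, compared by ANCOVA on baseline score, could be added as supportive. It should not be the required method: it treats an ordinal scale as interval, depends on the post-discharge rule, and gives no by-day result.

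The cost is one or two extra tables and a short missing-data rule. No new data collection is needed beyond what the protocol already asks for. The post-discharge rule needs care, since absence of a score after discharge is tied to recovery, and it should be fixed before unblinding.
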